6.4.6 Physical Examinations

A full physical examination, including height and weight, will be performed at scheduled time points as indicated in the [Table 1](#) of the protocol Section 1.3.

The full examination will include assessment of skin, head, ears, eyes, nose, throat, neck, thyroid, lungs, heart, cardiovascular system, abdomen, lymph nodes, and musculoskeletal system and extremities.

Any clinically significant finding identified during a study visit before administration of study vaccine will be recorded in the participant's medical history eCRF.

Any clinically significant finding identified during a study visit after administration of study vaccine will be reported as an MAAE.

Symptom-directed physical examinations may be performed at other time points at the discretion of the Investigator.

Summary tables or listing will not be provided for physical examinations.

6.4.7 Electrocardiogram (ECG)

12-lead ECG measurements will be recorded after 10 minutes of supine rest at Visit 1/Day 1 prior to vaccination. Summary table or listing will not be provided for ECG.

6.5 Immunogenicity Analysis

The analyses of immunogenicity will be based on the PP Set and will be performed by vaccination group and by age group.

If the number of participants in the FAS and PP Set differs (defined as the difference divided by the total number of participants in the PP Set) by more than 10% for each age

group, supportive analyses of immunogenicity may be conducted using the FAS. The supportive analysis is required if the condition is met.

The GMT and geometric mean (GM) level will be calculated using the following formula:

$$2^{\left\{ \frac{\sum_{i=1}^n \log_2(t_i)}{n} \right\}}$$

where t_1, t_2, \dots, t_n are n observed immunogenicity titers or levels.

The GMFR measures the changes in immunogenicity titers or levels within participants. The GMFR will be calculated using the following formula:

$$2^{\left\{ \frac{\sum_{i=1}^n \log_2(v_{ij}/v_{ik})}{n} \right\}} = 2^{\left\{ \frac{\sum_{i=1}^n \log_2(v_{ij}) - \log_2(v_{ik})}{n} \right\}}$$

where, for n participants, v_{ij} and v_{ik} are observed immunogenicity titers or levels for participant i at time points j and $k, j \neq k$.

The 95% CIs for GMT and GMFR will be calculated based on the t distribution of the log-transformed values then back transformed to the original scale for presentation, unless otherwise specified. Reverse cumulative distribution plot will be generated.

The model-based GM titer will be estimated based on an analysis of covariance (ANCOVA) model. In the ANCOVA model, the log-transformed antibody titer at a post baseline timepoint (Day 29) are treated as a dependent variable, with the treatment group as an explanatory variable and the log-transformed baseline antibody titer as a covariate, adjusting for the stratification factor(s) as appropriate, that is, age groups (18 to 49 years old, and 50 to 75 years old of age).

The GMT will be estimated by the geometric least square mean (GLSM) from the ANCOVA model for each treatment group and corresponding 95% CI will be provided.

For each pair of between-group comparison specified in [Table 3](#), the GMR (ratio of GMTs) between the two treatment groups in each pair will be estimated from the ANCOVA model, with 95% CI provided accordingly.

For each pair of between-group comparison specified in [Table 3](#), the difference of seroconversion rate (SCR) between the two treatment groups in each pair at Day 29 will be provided, with 95% CI estimated using Miettinen-Nurminen method.

Table 3 Exploratory Between-Group Immunogenicity Comparisons

Treatment Group	Group #1	Group #2	Group #3	Group #4	Group #5	Group #6	Group #7	Group #8
Group #1	NA	NA						
Group #2	NA	NA						
Group #3	#3 vs. #1	#3 vs. #2	NA	NA	NA	NA	NA	NA
Group #4	#4 vs. #1	#4 vs. #2	#4 vs. #3	NA	NA	NA	NA	NA
Group #5	#5 vs. #1	#5 vs. #2	#5 vs. #3	#5 vs. #4	NA	NA	NA	NA
Group #6	#6 vs. #1	#6 vs. #2	#6 vs. #3	#6 vs. #4	#6 vs. #5	NA	NA	NA
Group #7	#7 vs. #1	#7 vs. #2	#7 vs. #3	#7 vs. #4	#7 vs. #5	#7 vs. #6	NA	NA
Group #8	#8 vs. #1	#8 vs. #2	#8 vs. #3	#8 vs. #4	#8 vs. #5	#8 vs. #6	#8 vs. #7	NA

Note: The 8 treatment groups can be found in [Table 1](#) and the order might be re-arranged for easier reference.

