For the immunogenicity endpoints, geometric mean of specific antibody titers with corresponding 95% CI at each time point and geometric mean fold rise (GMFR) of specific antibody titers with corresponding 95% CI at each postbaseline time point over preinjection baseline at Day 1 will be provided by vaccination group. Descriptive summary statistics including median, minimum, and maximum will also be provided. Geometric mean titer (GMT) and GMFR might be adjusted for baseline titer and/or age group.

For summarizations of geometric mean titers, antibody titers reported as below lower limit of quantification (LLOQ) will be replaced by $0.5 \times LLOQ$. Values that are greater than the upper limit of quantification (ULOQ) will be converted to the ULOQ.

For HA, rate of seroconversion is defined as the proportion of participants with either a pre-vaccination HI titer < 1:10 and a postvaccination HI titer ≥ 1:40 or a prevaccination HI titer $\geq 1:10$ and a minimum 4-fold rise in postvaccination HI antibody titer. For NA, an endpoint of interest is the percentage of participants with a change in the Day 29 titer of at least 2-/3-/4-

fold rise, defined as $\geq 2-/3-/4$ -fold of the LLOQ if the Day 1 titer is < LLOQ; or $\geq 2-/3-/4$ -fold of the Day 1 titer if the Day 1 titer is \geq LLOQ.

Seroconversion rate from baseline will be provided with a 2-sided 95% CI using the Clopper-Pearson method at each postbaseline time point. For NA, the number and percentage of participants with $a \ge 2$ -, ≥ 3 -, and ≥ 4 -fold rise of serum titers from baseline will be provided with 2-sided 95% CI using the Clopper-Pearson method at each postbaseline time point.

Further details will be described in the SAP.

9.5.4. **Exploratory Analyses**

Exploratory analyses not addressed in Section 9.5.1 and Section 9.5.3 will be described in the SAP before database lock.

9.5.5. **Subgroup Analyses**

The protocol does not define any formal subgroup analyses. However, age-specific subgroup analyses may be performed to assess for potential differences in safety/reactogenicity or immune responses across age groups.

9.6. **Study Analyses**

One unblinded IA is planned in this study. It will be performed after participants have completed the Day 29 Visit and will include, at a minimum, cleaned data (ie, data that are as clean as possible) from available safety and immunogenicity datasets.

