4.2 Statistical Hypotheses

No formal hypotheses will be tested for this study.

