4.3 Sample Size and Power

The sample size for this trial is not driven by statistical assumptions for formal hypothesis testing. The number of proposed participants is considered sufficient to provide a descriptive summary of the safety and immunogenicity of different dose levels of mRNA-1020 or mRNA-1030.

A total of approximately 560 participants will be randomly assigned to receive mRNA-1020, mRNA-1030, mRNA-1010, or Flublok. Among those ~560 participants, 70 participants will be randomized into each vaccination group. Details regarding the number of participants in each vaccination group and the randomization ratio are presented in [Table 1](#). With 70 participants in each group receiving the IP, there is an approximately 76% probability to observe at least 1 participant with an AE if the true incidence of the AE is 2%; if the true incidence rate is 4%, then the probability to observe an AE is approximately 94%.

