6.2.10 Adjustment for Covariates

The estimates of GMFR with 95% CIs will be calculated based on analysis of covariance (ANCOVA) model adjusted for baseline titer, age group and /or other covariates. Antibody titers are analyzed using \log_2 titers or \log_2 fold rise and back transformed to estimate GMFRs with 95% CIs. After transformation, the data tend to be normally distributed.

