6.5.3 Secondary Analysis of Immunogenicity

For each vaccination group, the following evaluations will be performed at all evaluable humoral immunogenicity time points.

GMTs and GMFRs:

- GMT of vaccine-matched strain-specific anti-HA antibodies with corresponding 95% CI will be provided at each time point,. Geometric mean (GM) level and corresponding 95% CI will be plotted at each time point.
- GMT of vaccine-matched strain-specific anti-NA antibodies with corresponding 95% CI will be provided at each time point.GM level and corresponding 95% CI will be plotted at each time point.
- GMFR of vaccine-matched strain-specific anti-HA antibodies with corresponding 95% CI will be provided at each post-baseline time point over pre-injection baseline at Day 1. GMFR and corresponding 95% CI will be plotted at each time point.
- GMFR of vaccine-matched strain-specific anti-NA antibodies with corresponding 95% CI will be provided at each post-baseline time point over pre-injection

baseline at Day 1. GMFR and corresponding 95% CI will be plotted at each time point.

- In addition, the following descriptive statistics will also be provided at each time point: the number of participants (n), median, minimum, and maximum.
- Reverse cumulative distribution function curve at each time point will be provided.
- Listing of anti-HA antibodies for vaccine-matched seasonal influenza A and B strains will be provided based on the PP Set.
- Listing of anti-HA antibodies for vaccine-matched seasonal influenza A and B strains for participants with influenza infection will be provided based on the PP Set.
- Listing of anti-NA antibodies for vaccine-matched seasonal influenza A and B strains will be provided based on the PP Set.
- Listing of anti-NA antibodies for vaccine-matched seasonal influenza A and B strains for participants with influenza infection will be provided based on the PP Set.

Seroconversion:

For each vaccination group, the following evaluations will be performed at each post-baseline time point.

- For HA, the number and percentage of participants with seroconversion at each post-baseline time point will be provided with 2-sided 95% CI using the Clopper-Pearson method.

2-/3-/4-fold Rise:

For NA: For each vaccination group, the following evaluations will be performed at each post-baseline time point.

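### The adjusted GMT model and the Table 3 ratios are specified at Day 29 only, so the secondary Day 8 and Day 181 GMTs are unadjusted and have no between-arm ratio

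*SAP*

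**What the plan says.** **GMT and GMR.** SAP 6.5 sets the default interval for both GMT and GMFR as a t interval on log values. It then adds a model-based GMT in which "the log-transformed antibody titer at a post baseline timepoint (Day 29) are treated as a dependent variable", with "the log-transformed baseline antibody titer as a covariate, adjusting for the stratification factor(s) as appropriate". The least-squares GMTs and the pairwise GMRs of Table 3 (titled exploratory) are taken from this model. Differences in seroconversion rate for the same pairs are also set at Day 29.

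**Secondary analysis.** SAP 6.5.3 covers all humoral time points, which are Day 1, 8, 29 and 181 in the Schedule of Events. It says "GMT of vaccine-matched strain-specific anti-HA antibodies with corresponding 95% CI will be provided at each time point", has a parallel line for anti-NA, and names no model. It also lists GMFR, seroconversion and 2-/3-/4-fold rise at each post-baseline visit.

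**GMFR.** SAP 6.2.10 says "The estimates of GMFR with 95% CIs will be calculated based on analysis of covariance (ANCOVA) model adjusted for baseline titer, age group" and leaves further covariates open. It names no visit. SAP 6.5 separately defines GMFR as the back-transformed mean log fold rise.

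**Protocol.** Section 9.5.3 says "Geometric mean titer (GMT) and GMFR might be adjusted for baseline titer and/or age group", with no visit limit. SAP 4.2 says "No formal hypotheses will be tested for this study".

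**The concern.** GMT at all humoral visits is a secondary endpoint (SAP 3.2), and Day 181 is the only measure of persistence. At Day 29 the sponsor judged it worthwhile to adjust for baseline titer and age and to give pairwise ratios. Nothing explains why this stops at the other visits, although PP Set membership already requires a baseline sample and age group is known for everyone.

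The study is meant to identify a candidate for pivotal work (Protocol 2.1), so readers will compare arms at Day 181 whether or not a ratio is tabulated. They would do so from raw GMTs with wider intervals than necessary, next to Day 29 estimates for the same arms that have been adjusted. Stratified randomization balances age but not baseline titer.

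For GMFR the question is which of two written methods applies. If this is left open, it would be settled after prespecified sponsor staff have seen unblinded Day 29 results at the interim analysis (Protocol 9.1 and 9.6).

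**Working it through.** **1. The plan's own figure.** The only sample-size arithmetic is in SAP 4.3: "With 70 participants in each group receiving the IP, there is an approximately 76% probability to observe at least 1 participant with an AE" at 2% incidence, and "if the true incidence rate is 4%, then the probability to observe an AE is approximately 94" per cent. Check: 1 − 0.98^70 = 0.757 and 1 − 0.96^70 = 0.943. Both reproduce. They concern adverse events; the plan states no precision target for titers.

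**2. Which estimator applies at which visit.**

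| Quantity | Day 29 | Day 8 and Day 181 |
|---|---|---|
| GMT by arm | Raw with t interval, plus adjusted GMT from ANCOVA (6.5) | Raw with t interval only (6.5.3, with the 6.5 default) |
| GMT ratio between arms | Table 3 pairs from ANCOVA | None |
| GMFR by arm | Adjusted (6.2.10) or raw formula (6.5), not reconciled | Same two, not reconciled |
| Seroconversion, fold rise | Proportions by arm; Table 3 differences for seroconversion | Proportions by arm |

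**3. Precision.** Let ρ be the within-arm correlation between log2 baseline and later log2 titer. It is not in the documents and is assumed here. The ratio of adjusted to unadjusted interval width on the log scale is about √(1 − ρ²):

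- ρ = 0.3: 0.954 (5% narrower)
- ρ = 0.5: 0.866 (13% narrower)
- ρ = 0.7: 0.714 (29% narrower)
- ρ = 0.8: 0.600 (40% narrower)

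**4. Chance baseline imbalance.** Assume SD 2.0 log2 at both visits, so that the slope equals ρ, and 70 per arm. The SE of the baseline difference between two arms is 2.0 × √(2/70) = 0.338 log2. A one-SE imbalance moves a ratio of raw GMTs by ρ × 0.338 log2:

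- ρ = 0.3: 0.101 log2, 1.07-fold
- ρ = 0.5: 0.169 log2, 1.12-fold
- ρ = 0.7: 0.237 log2, 1.18-fold

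The unadjusted 95% half-width for such a ratio is 1.96 × 0.338 = 0.663 log2, or 1.58-fold, so these shifts lie inside it. The same imbalance moves a ratio of raw GMFRs the other way, by −(1 − ρ) × 0.338 log2. At ρ = 0.5 that is −0.169 log2, or 0.89-fold. The two raw summaries can therefore point in opposite directions by chance; ANCOVA accounts for the imbalance in both.

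**5. Does an adjusted GMFR already supply the answer?** Log fold rise is later log titer minus baseline log titer. With baseline as a covariate, switching the outcome from titer to fold rise lowers the baseline coefficient by 1 and changes nothing else. In a simulated data set of 8 arms of 70, the arm contrasts and standard errors were identical. So 6.2.10 would carry the same between-arm information if it is applied at Day 8 and Day 181, with the same covariates, and the contrasts are reported. The SAP does not settle the first point against 6.5, leaves the covariates open, and does not plan the contrasts at those visits.

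**The case against.** The strongest reply is that adjustment is not confined to Day 29. SAP 6.2.10 sets an adjusted GMFR without a visit limit, 6.5.3 reports GMFR at every post-baseline visit, and step 5 shows that the two models give the same contrasts. The t interval in 6.5 is only a default, so 6.2.10 can be read as overriding it for GMFR. This stands, and it limits the point to GMT, GMR and an unreconciled GMFR method. It does not close the gap, because 6.2.10 provides no adjusted GMT and no arm contrast with an interval.

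A reader might infer that persistence would rest on raw GMTs alone. The documents do not support that: GMFR, seroconversion and fold rise are also planned at each visit, and all use the participant's own baseline.

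A reader might also infer that the planned Day 181 results are biased. They are not. A raw GMT is a valid description of its arm, chance imbalance under randomization is already covered by the unadjusted interval, and no Day 181 GMT ratio is planned that would carry the shifts in step 4. Age is a stratum, and results are also shown by age group.

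Finally, the study tests no hypotheses and Table 3 is exploratory. Its 2 + 3 + 4 + 5 + 6 + 7 = 27 pairs, over 4 strains, 2 assays and 2 more visits, would add 27 × 4 × 2 × 2 = 432 ratios. That is a real though small cost. It does not explain why the same ratios are useful at Day 29 but not later.

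**Conclusion.** The point holds for GMT and the Table 3 GMRs. As written, their adjusted model is tied to Day 29, and the secondary Day 8 and Day 181 GMTs default to unadjusted geometric means with t intervals and no between-arm ratio. For GMFR the fault is different: adjustment is planned without a visit limit, but it sits beside a raw formula and the SAP does not say which is reported at each visit.

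The size depends on a correlation that the documents do not give. Over an assumed 0.3 to 0.8, adjusted log-scale intervals would be about 5% to 40% narrower; at the low end the gain is slight. The fold shifts in step 4 also assume SD 2.0 log2 at both visits and 70 per arm, and they illustrate noise rather than error in any planned result. The benefit is precision and consistency with Day 29. No primary Day 29 result is affected.

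**What to change.** In SAP 6.5 and 6.5.3, state that the Day 29 ANCOVA (log2 titer on arm, log2 baseline titer and age stratum) is also fitted at Day 8 and Day 181. Report the least-squares GMTs and the exploratory Table 3 GMRs with 95% CIs beside the raw GMTs. Add a sentence that 6.2.10 governs the adjusted GMFR at each post-baseline visit, and label the formula in 6.5 as the raw summary.

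Protocol 9.5.3 already permits this adjustment, so no protocol change is needed. The cost is a few lines of SAP text, re-use of the Day 29 code and additional exploratory tables. No new data or samples are required.

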4.4 Randomization

Approximately 560 participants will be randomized in a 1:1:1:1:1:1:1 ratio to receive either mRNA-1020 ~~CCI~~, mRNA-1020 ~~CCI~~, mRNA-1020 ~~CCI~~, mRNA-1030 ~~CCI~~, mRNA-1030 ~~CCI~~, mRNA-1030 ~~CCI~~, mRNA-1010 50 μ g, or Flublok 180 μ g, with approximately 70 healthy adult participants randomly assigned to each vaccination group. Randomization will be stratified by age (18 to < 50 years versus \geq 50 to \leq 75 years) and will be balanced across the 2 age groups within each vaccination group.

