6.2.9 Age and Vaccination Groups

Age groups:

The following age groups will be used for summary purposes:

- Overall
- Age: ≥ 18 to < 50 years
- Age: ≥ 50 to ≤ 75 years

Vaccination groups:

The following vaccination groups will be used for summary purposes:

- mRNA-1030 CCI
- mRNA-1020 CCI
- mRNA-1030 CCI
- mRNA-1020 CCI
- mRNA-1030 CCI
- mRNA-1020 CCI
- mRNA-1010 50 μg
- Flublok 180 μg

All analyses and data summaries/displays will be provided by vaccination group (and then by age group) using appropriate analysis population, unless otherwise specified.

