6.10 Subgroup Analysis

The protocol does not define any formal subgroup analyses, and the study is not adequately powered to perform formal subgroup analyses. However, age-specific subgroup analyses may be performed to explore for potential differences in safety/reactogenicity or immune responses across age groups.

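### SAP 6.5 names no age strata for the exploratory seroconversion-rate differences, although randomisation is stratified by age and the ANCOVA for the matching GMRs adjusts for it

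*SAP*

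**What the plan says.** SAP 4.4 states that "Randomization will be stratified by age", with strata 18 to <50 and 50 to 75 years.

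SAP 6.5 plans two contrasts for each pair of arms in Table 3, which is titled "Exploratory Between-Group Immunogenicity Comparisons":

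- For titers, "the GMR (ratio of GMTs) between the two treatment groups in each pair will be estimated from the ANCOVA model". That model has log baseline titer as a covariate and is described as "adjusting for the stratification factor(s) as appropriate, that is, age groups".
- For seroconversion, the difference in rates "at Day 29 will be provided, with 95% CI estimated using Miettinen-Nurminen method". No strata, weights or covariates follow.

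Nothing elsewhere fills the gap. SAP 6.2.10 (covariate adjustment) concerns the GMFR only. Protocol 9.5.3 allows for possible adjustment of the GMT and GMFR and does not mention rate differences. SAP 6.2.9 and 6.5 plan displays by vaccination group and by age group, and SAP 6.10 adds that "age-specific subgroup analyses may be performed to explore for potential differences". None of these describes a combined, age-weighted seroconversion difference.

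**The concern.** Two contrasts for the same pair of arms would be reported side by side, one with age in the model and the other apparently without it. Two consequences follow.

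- **Precision.** If seroconversion differs by age, a crude interval ignores variation that the design has already controlled, so it is wider than it needs to be.
- **Age mix.** These analyses use the Per-Protocol Set. Randomisation balances age among those randomised, but exclusions for sampling times, influenza infection or deviations can unbalance it. The crude difference then partly reflects age.

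Table 3 lists 27 pairs. With 4 vaccine-matched strains that makes 108 overall differences. They are exploratory, but protocol 2.1 expects the study to identify a candidate to take forward, so they are likely to be read closely.

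**Working it through.** **The plan's own figure.** The SAP gives no precision figure for seroconversion differences. Its only design calculation (SAP 4.3) is the chance of seeing at least one AE among 70 participants. It reproduces: 1 - 0.98^70 = 75.7% and 1 - 0.96^70 = 94.3%, against the stated 76% and 94%.

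**Inputs from the documents.** 70 per arm (SAP 4.3), 35 + 35 by age (protocol Table 4), 4 strains (SAP 4.1). Table 3 pairs, counted by row: 2 + 3 + 4 + 5 + 6 + 7 = 27, and 27 × 4 = 108.

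**Assumptions.** Overall seroconversion of 60% versus 50%, with the same younger-minus-older gap in both arms, varied from 0 to 40 points.

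**Method.** The unstratified limits are the values δ at which (d - δ)² / V(δ) = 1.96². V(δ) uses the restricted maximum-likelihood rates and the factor N/(N - 1). The stratified limits solve [Σ w_k(d_k - δ)]² / Σ w_k² V_k(δ) = 1.96², with w_k proportional to n1k·n2k/(n1k + n2k). With 35 in every cell each stratum has weight 35·35/70 = 17.5, that is one half.

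**Width at expected counts.** The unstratified interval is -6.5 to 26.0 points, half-width 16.24, at every age gap.

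| Age gap (points) | Stratified half-width | Change in width |
|---|---|---|
| 0 | 16.30 | +0.4% |
| 10 | 16.23 | -0.1% |
| 20 | 16.00 | -1.5% |
| 30 | 15.62 | -3.9% |
| 40 | 15.06 | -7.3% |

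At 55% versus 55% the changes are nearly the same: +0.4, -0.1, -1.5, -3.8 and -7.2%. The small penalty at gap 0 comes from applying N/(N - 1) within strata: √[(70/69)/(140/139)] = 1.0036.

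**Coverage.** The unstratified interval covers 95.1% at gap 0, rising to 96.8% at gap 40. The stratified interval stays between 94.9% and 95.3%. The crude interval is therefore valid and becomes conservative as the age effect grows.

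**Shift from age imbalance in the Per-Protocol Set.** Shift = gap × (younger share in one arm - younger share in the other).

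| Younger/older, arm 1 vs arm 2 | Difference in younger share | Shift at gaps of 10 to 40 points |
|---|---|---|
| 35/35 vs 35/32 | 0.500 vs 0.522 | 0.2 to 0.9 points |
| 35/32 vs 32/35 | 0.522 vs 0.478 | 0.4 to 1.8 points |
| 35/28 vs 28/35 | 0.556 vs 0.444 | 1.1 to 4.4 points |

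The stratified difference stays at 10.0 points in all of these.

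**Within-age displays.** At 35 versus 35 and 60% versus 50% the half-width is about 22.8 points, close to 16.24 × √2 = 23.0. The separate age-group results are thus much less precise than the overall one and do not replace it.

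**The case against.** The strongest reply is that this is a preference between two acceptable analyses. The contrasts are labelled exploratory, "No formal hypotheses will be tested for this study", and the crude interval has at least nominal coverage in the scenarios run. No error rate, sample size or primary result changes. All of that stands.

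Other points have partial force:

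- The age term in the ANCOVA is itself qualified by the words on appropriateness. This softens the contrast between the two analyses, but the SAP still names age for one and is silent for the other.
- The SAP does not say the method is unstratified, and Miettinen-Nurminen exists in both forms. At the least, the form should be stated.
- Within-age comparisons are planned. A reader could combine the two point estimates from them, but not obtain the interval.
- The gain is not universal. At 90% versus 85% the width changes by only +0.4, +0.1 and -0.2% at gaps of 0, 10 and 20 points. At 10% versus 5% with a 10-point gap, where one cell has no responders, the stratified interval is 1.15% wider.
- When the age mix differs by arm, the stratified difference no longer equals the difference between the tabulated per-arm rates.
- The larger figures need a 40-point age gap, and the 4.4-point shift also needs opposite 20% losses by age (7 of 35). The documents suggest neither.

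**Conclusion.** The point holds as an optional improvement to an exploratory analysis. The SAP names age for the GMRs and gives no strata or weights for the seroconversion differences of the same pairs, and no other section supplies a pooled age-stratified difference.

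The benefit is modest. In the mid-range scenarios the precision gain is at most 1.5% of interval width for age gaps up to 20 points and reaches about 7% only at 40 points. The more useful gains are protection against age imbalance in the Per-Protocol Set, worth 0.2 to 0.9 points when one arm loses 3 older participants, and consistency with the randomisation and the GMR model. The primary per-arm Clopper-Pearson results are unaffected.

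All sizes rest on assumed seroconversion rates, age gaps and exclusion patterns, because the documents give none. The textual finding does not depend on them.

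**What to change.** Add one sentence to SAP 6.5: for the overall population, each Table 3 seroconversion-rate difference and its 95% CI use the stratified Miettinen-Nurminen method, with the randomisation age groups (18 to <50 and 50 to 75 years) as strata and Mantel-Haenszel weights n1k·n2k/(n1k + n2k). Keep the unstratified form for the displays within each age group. A table footnote should say that the stratified difference may not equal the difference between the tabulated rates.

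The cost is that sentence and a standard programming option, with no new data or participants. With no age effect and balanced ages the interval is about 0.4% wider. The largest penalty seen in any scenario was about 1%.
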